9.1.4 Lost to follow-up

For participants whose status is unclear because they fail to appear for study visits without stating an intention to discontinue or withdraw, the investigator must show "due diligence" by documenting in the source documents steps taken to contact the subject, e.g. dates of telephone calls, registered letters, etc. A subject should not be considered as lost to follow-up until due diligence has been completed. Participants lost to follow up should be recorded as such on the appropriate eCRF page.

9.1.5 Early study termination by the sponsor

The study can be terminated by Novartis at any time.

Reasons for early termination:

- Unexpected, significant, or unacceptable safety risk to participants enrolled in the study
- Decision based on recommendations from applicable board(s) after review of safety and efficacy data
- Discontinuation of study drug development

In taking the decision to terminate, Novartis will always consider participant welfare and safety. Should early termination be necessary, participants must be seen as soon as possible and treated as a participant who discontinued from study treatment: Novartis will provide instruction for contacting the participant, when the participant should stop taking drug, when the participant should come in for a final visit(s) that the safety follow up period must be completed and which visits to be performed. The investigator may be informed of additional procedures to be followed in order to ensure that adequate consideration is given to the protection of the participant's interests. The investigator or sponsor depending on local regulation will be responsible for informing IRBs/IECs of the early termination of the trial.

9.2 Study completion and post-study treatment

For participants, study completion is defined as when the subject has completed the 30 day safety follow-up.

Final analysis will be performed when all the participants complete the treatment period or discontinue early, and final CSR will be written.

Participants will continue to receive study treatment until reasons for discontinuation of study treatment are met in [Section 9.1.1](#) or treatment completion. In addition, participants may voluntarily withdraw from the study treatment or may be taken off the study treatment at the discretion of the investigator at any time.

10 Safety monitoring and reporting

10.1 Definition of adverse events and reporting requirements

10.1.1 Adverse events

An adverse event (AE) is any untoward medical occurrence (e.g. any unfavorable and unintended sign [including abnormal laboratory findings], symptom or disease) in a clinical investigation participant after providing written informed consent for participation in the study. Therefore, an AE may or may not be temporally or causally associated with the use of a medicinal (investigational) product.

The investigator has the responsibility for managing the safety of individual participant and identifying adverse events.

Novartis qualified medical personnel will be readily available to advise on trial related medical questions or problems.

The occurrence of adverse events must be sought by non-directive questioning of the participant at each visit during the study. Adverse events also may be detected when they are volunteered by the participant during or between visits or through physical examination findings, laboratory test findings, or other assessments.

Adverse events must be recorded under the signs, symptoms, or diagnosis associated with them, accompanied by the following information (as far as possible) (if the event is serious refer to [Section 10.1.2](#)):

Adverse events will be assessed and graded according to the Common Terminology Criteria for Adverse Events (CTCAE) version 5.0.

- Its relationship to the study treatment. If the event is due to lack of efficacy or progression of underlying illness (i.e. progression of the study indication) the assessment of causality will usually be 'Not suspected.' The rationale for this guidance is that the symptoms of a lack of efficacy or progression of underlying illness are not caused by the trial drug, they happen in spite of its administration and/or both lack of efficacy and progression of underlying disease can only be evaluated meaningfully by an analysis of cohorts, not on a single participant
- Its duration (start and end dates or ongoing) and the outcome must be reported
- Whether it constitutes a SAE (see [Section 10.1.2](#) for definition of SAE) and which seriousness criteria have been met
- Action taken regarding with study treatment. All adverse events must be treated appropriately. Treatment may include one or more of the following:
 - Dose not changed
 - Dose Reduced/increased
 - Drug interrupted/permanently discontinued
- Its outcome (not recovered/not resolved; recovered/resolved; recovered/resolved with sequelae; fatal or unknown).

If the event worsens the event should be reported a second time in the CRF noting the start date when the event worsens in toxicity. For grade 3 and 4 adverse events only, if improvement to a lower grade is determined a new entry for this event should be reported in the CRF noting the start date when the event improved from having been Grade 3 or Grade 4.

Conditions that were already present at the time of informed consent should be recorded in medical history of the participant.

Adverse events (including lab abnormalities that constitute AEs) should be described using a diagnosis whenever possible, rather than individual underlying signs and symptoms.

Adverse event monitoring should be continued for at least 30 days following the last dose of study treatment.

Once an adverse event is detected, it must be followed until its resolution or until it is judged to be permanent (e.g. continuing at the end of the study), and assessment must be made at each visit (or more frequently, if necessary) of any changes in severity, the suspected relationship to the interventions required to treat it, and the outcome.

Progression of malignancy (including fatal outcomes), if documented by use of appropriate method (for example, as per RECIST criteria), should not be reported as a serious adverse event, except if the investigator considers that progression of malignancy is related to study treatment.

Adverse events separate from the progression of malignancy (i.e. deep vein thrombosis at the time of progression or hemoptysis concurrent with finding of disease progression) will be reported as per usual guidelines used for such events with proper attribution regarding relatedness to the drug.

Abnormal laboratory values or test results constitute adverse events only if they fulfill at least one of the following criteria:

- they induce clinical signs or symptoms
- they are considered clinically significant
- they require therapy

Clinically significant abnormal laboratory values or test results must be identified through a review of values outside of normal ranges/clinically notable ranges, significant changes from baseline or the previous visit, or values which are considered to be non-typical in participant with the underlying disease.

10.1.2 Serious adverse events

An SAE is defined as any adverse event [appearance of (or worsening of any pre-existing)] undesirable sign(s), symptom(s), or medical condition(s) which meets any one of the following criteria:

- fatal
- life-threatening

Life-threatening in the context of a SAE refers to a reaction in which the participant was at risk of death at the time of the reaction; it does not refer to a reaction that hypothetically might have caused death if it were more severe (please refer to the ICH-E2D Guidelines).

- results in persistent or significant disability/incapacity
- constitutes a congenital anomaly/birth defect
- requires inpatient hospitalization or prolongation of existing hospitalization, unless hospitalization is for:
 - routine treatment or monitoring of the studied indication, not associated with any deterioration in condition
 - elective or pre-planned treatment for a pre-existing condition that is unrelated to the indication under study and has not worsened since signing the informed consent
 - social reasons and respite care in the absence of any deterioration in the participant's general condition
 - treatment on an emergency outpatient basis for an event not fulfilling any of the definitions of a SAE given above and not resulting in hospital admission
- is medically significant, e.g. defined as an event that jeopardizes the participant or may require medical or surgical intervention to prevent one of the outcomes listed above

Medical and scientific judgment should be exercised in deciding whether other situations should be considered serious reactions, such as important medical events that might not be immediately life threatening or result in death or hospitalization but might jeopardize the participant or might require intervention to prevent one of the other outcomes listed above. Such events should be considered as "medically significant." Examples of such events are intensive treatment in an emergency room or at home for allergic bronchospasm, blood dyscrasias, or convulsions that do not result in hospitalization or development of dependency or abuse (please refer to the ICH-E2D Guidelines).

All new malignant neoplasms will be assessed as serious under "medically significant" if other seriousness criteria are not met and the malignant neoplasm is not a disease progression of the study indication.

Any suspected transmission via a medicinal product of an infectious agent is also considered a serious adverse reaction.

All reports of intentional misuse and abuse of the product are also considered serious adverse event irrespective if a clinical event has occurred.

10.1.3 SAE reporting

[figure not shown]
To ensure participant safety, every SAE, regardless of causality, occurring after the participant has provided informed consent and until 30 days following the last administration of study treatment must be reported to Novartis safety immediately, without undue delay, under no circumstances later than 24 hours of learning of its occurrence. Detailed instructions regarding the submission process and requirements are to be found in the investigator folder provided to each site.

If a new antineoplastic therapy is initiated during the 30-day safety follow-up period, only SAEs suspected to be related to the study treatment will be collected in the AE eCRF.

The following SAE reporting timeframes apply:

- Screen failures (e.g. a participant who is screened but is not treated): SAEs occurring after the participant has provided informed consent until the time the participant is deemed a screen failure must be reported to Novartis.
- Enrolled OR Treated Participants: All SAEs collected between time participant signs ICF until 30 days after the participant has permanently stopped study treatment

All follow-up information for the SAE including information on complications, progression of the initial SAE and recurrent episodes must be reported as follow-up to the original episode within 24 hours of the investigator receiving the follow-up information. An SAE occurring at a different time interval or otherwise considered completely unrelated to a previously reported one must be reported separately as a new event.

Suspected Unexpected Serious Adverse Reactions (SUSARs) will be collected and reported to the competent authorities and relevant ethics committees in accordance with EU Guidance 2011/C 172/01 or as per national regulatory requirements in participating countries.

Any SAEs experienced after the 30 day follow-up period should only be reported to Novartis Safety if the investigator suspects a causal relationship to study treatment.

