6.5.1 Treatment interruption and treatment discontinuation

If the administration of capmatinib is temporarily interrupted for reasons other than toxicity, then treatment with capmatinib may be resumed at the same dose. If the treatment with capmatinib is withheld due to toxicity, the dose modification guidelines in [Table 6-3](#) & [Table 6-2](#) should be followed. In any case, scheduled visits and all assessments (including tumor assessments) should continue to be performed, as described in [Table 8-1](#).

If the treatment with capmatinib is withheld for more than 21 consecutive days (counting from the first day when a dose was interrupted), excluding the surgical and adjuvant chemotherapy

window specified below, then capmatinib should be permanently discontinued. Under exceptional circumstance, when the investigator believes that continuing treatment may still derive clinical benefit for the participant, study treatment may be resumed. However, the investigator must discuss and receive approval from Novartis Medical Lead or designee prior to continuing capmatinib treatment.

Participants who discontinue the study due to a study drug related AE or an abnormal laboratory value must be followed as described in [Section 6.5.2](#).

After the 8 week neoadjuvant treatment with capmatinib, participants are to undergo surgical resection. Participants should undergo within 2 weeks after last dose of neoadjuvant capmatinib. In addition, participants may receive adjuvant chemotherapy prior to re-starting capmatinib at the discretion of the investigator. For patients who do not receive adjuvant chemotherapy no more than 10 weeks should elapse from the date of surgery and the start of adjuvant capmatinib. For patients who do receive adjuvant chemotherapy, see [Section 6.2.1.1](#) for the dosing window. If participants for any reason cannot re-start capmatinib therapy within the specified windows, then study treatment must be permanently discontinued.

Participants who discontinue the study due to a surgery related AE must complete the EOT visit and safety follow-up visit.

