6.5.2 Follow-up for toxicities

All participants will be followed for safety until 30 days after the last dose of capmatinib. Participants whose treatment is temporarily interrupted or permanently discontinued due to a toxicity AE or abnormal laboratory value must be followed until resolution or stabilization of the event, whichever comes first, including all study assessments appropriate to monitor the event.

An unscheduled assessment should be performed in all cases below where toxicity monitoring is recommended more frequently than defined by the schedule of assessments. Subsequent monitoring must be performed as per the regular visit schedule. Please refer to [Table 6-4](#) for follow-up evaluations for selected toxicities.

Table 6-4 Follow-up evaluations for selected toxicities

TOXICITY	FOLLOW-UP EVALUATION
HEMATOLOGICAL	
Febrile neutropenia, Neutropenia \geq CTCAE grade 3	
• Test weekly (or more frequently if clinically indicated) until \leq CTCAE grade 2.
Thrombocytopenia \geq CTCAE grade 3	
Anemia \geq CTCAE grade 3	
• Perform physical exam for check on bruising in case of major thrombocytopenia.
RENAL	
Serum creatinine \geq CTCAE grade 2	
• Test weekly (or more frequently if clinically indicated) until \leq CTCAE grade 1 or baseline.• Participants will be instructed to increase hydration until resolution to \leq CTCAE grade 1 or baseline.

TOXICITY	FOLLOW-UP EVALUATION
HEPATIC	

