Table 8-1 Assessment schedule

Period	Screening	Treatment		Surgery		Treatment		Follow-up	
		Cycle 1	Cycle 2			Cycle 3 & beyond up to 3 years			
Visit Name	Screening	Treatment C1D1	Treatment C2D1	Surgery	Post-surgery	Treatment C3D1	Treatment C4D1 & beyond	EOT	30 day safety follow up
Days/months	-28 to -1	1	28	Within 2 weeks from last dose of capmatinib ⁶	2 weeks from date of surgery ⁹	10-26 weeks from surgery ³	Every 3 months	when applicable	30 days post last dose of capmatinib
Electrocardiogram (ECG)	X	X ²		If clinically indicated				X	
Pulmonary function tests (PFT)	X ⁴			X ⁵	X				
Hematology blood sample	X	X	X		X	X	X	X	X
Chemistry blood sample	X	X	X		X	X	X	X	X
Coagulation panel	X		If clinically indicated						
Urinalysis (dipstick)	X	X	X			X	X		

Period	Screening	Treatment		Surgery		Treatment		Follow-up									
		Cycle 1	Cycle 2			Cycle 3 & beyond up to 3 years											
Visit Name	Screening	Treatment C1D1	Treatment C2D1	Surgery	Post-surgery	Treatment C3D1	Treatment C4D1 & beyond	EOT	30 day safety follow up								
Days/months	-28 to -1	1	28	Within 2 weeks from last dose of capmatinib ⁶	2 weeks from date of surgery ⁹	10-26 weeks from surgery ³	Every 3 months	when applicable	30 days post last dose of capmatinib								
Prior/concomitant medications	X	X (Continuous from 28 days prior to starting treatment until 30 day safety follow-up or start of new antineoplastic medication (ANP), whichever is sooner)															
Non-drug therapies and procedures	X	X (Continuous from 28 days prior to starting treatment until 30 day safety follow-up or start of new antineoplastic medication (ANP), whichever is sooner)															
Adverse Events	X (Continuous until ≥ 30 days after the last dose of INC280)																
Serious Adverse Events	X (Continuous until ≥ 30 days after the last dose of INC280)																
Serum pregnancy test	S (within 72 hours prior to first dose)							S ¹¹	S ¹¹								
Urine pregnancy test ¹¹			S			S	S										

Period	Screening	Treatment		Surgery		Treatment		Follow-up								
		Cycle 1	Cycle 2			Cycle 3 & beyond up to 3 years										
Visit Name	Screening	Treatment C1D1	Treatment C2D1	Surgery	Post-surgery	Treatment C3D1	Treatment C4D1 & beyond	EOT	30 day safety follow up							
Days/months	-28 to -1	1	28	Within 2 weeks from last dose of capmatinib ⁶	2 weeks from date of surgery ⁹	10-26 weeks from surgery ³	Every 3 months	when applicable	30 days post last dose of capmatinib							
Surgery				X												

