PET-CT (with diagnostic quality CT)	X ¹⁰															
CT/MRI – Chest	X ¹⁰			X, To be performed within 7 days prior to surgery	X, At the initiation of adjuvant therapy (chemotherapy or capmatinib) and every 12 weeks for the first year of treatment, every 26 weeks thereafter ⁷											
Brain MRI	X			If clinically indicated												
Whole body bone scan		If clinically indicated														
Tumor sample from surgery ¹				X												

Period	Screening	Treatment		Surgery		Treatment		Follow-up	
		Cycle 1	Cycle 2			Cycle 3 & beyond up to 3 years			
Visit Name	Screening	Treatment C1D1	Treatment C2D1	Surgery	Post-surgery	Treatment C3D1	Treatment C4D1 & beyond	EOT	30 day safety follow up
Days/months	-28 to -1	1	28	Within 2 weeks from last dose of capmatinib ⁶	2 weeks from date of surgery ⁹	10-26 weeks from surgery ³	Every 3 months	when applicable	30 days post last dose of capmatinib
MPR				X					
Adjuvant chemotherapy ⁸					X				
Study drug administration (capmatinib)		X (continuous twice daily (BID) dosing)				X (continuous twice daily (BID) dosing)			
Antineoplastic therapies since discontinuation of study treatment									X

X = assessment to be recorded in the clinical database or received electronically from a vendor

S = assessment to be recorded in the source documentation only

¹ Lymph nodes might be requested if collected, see [Table 8-6](#) for number of unstained slides.

² pre-dose

³ No more than 26 weeks or 10 weeks can elapse between surgery and start of adjuvant capmatinib for patients who have or have not received adjuvant chemotherapy, respectively.

⁴ Within 3 months before starting neoadjuvant capmatinib

⁵ After neoadjuvant capmatinib but before surgery

⁶ Delay to the surgical procedure beyond 2 weeks is acceptable, but should be avoided. Please contact the sponsor if surgery will be beyond the 2 week window.

⁷ Post-surgery scan schedule to start with initiation of any adjuvant treatment, chemotherapy or capmatinib.

⁸ Standard postoperative adjuvant chemotherapy, consisting of a platinum-based doublet for 4 cycles is allowed. No more than 26 weeks can elapse between surgery and start of adjuvant capmatinib.

⁹ Post-surgery visit to be approximately 2 weeks from date of surgery in alignment with practice guidelines.

¹⁰ Chest CT/MRI or PET-CT (with diagnostic quality CT) is required at baseline.

¹¹ For women of child-bearing potential only

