8.6 Follow up evaluations

8.6.1 Safety follow up

All subjects will be followed for AEs and SAEs for at least 30 days following the EOT visit. At the end of this period, the investigator should assess and discuss with the subject any AEs observed and concomitant medications taken since discontinuation of study treatment. Subjects whose treatment is permanently discontinued due to an AE (clinical or based on abnormal laboratory value) must be followed until resolution or stabilization of the event, whichever

comes first. In case of an abnormal laboratory value, blood tests should be repeated until resolution or stabilization. See [Table 8-1](#) for list of assessments to be performed at safety follow-up visit.

If a new antineoplastic therapy is initiated after discontinuation of study treatment, only SAEs suspected to be related to study treatment will be collected in the Adverse Events eCRF.

9 Discontinuation and completion

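### The 30-day end of AE/SAE collection has three different starting points, and they diverge for a participant who does not restart capmatinib after surgery

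*Protocol*

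**What the plan says.** The protocol sets the end of safety collection in several places.

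- **Last dose, hard end.** Section 6.5.2: "All participants will be followed for safety until 30 days after the last dose of capmatinib". The first paragraph of 10.1.3 requires SAEs to be reported "until 30 days following the last administration of study treatment must be reported to Novartis safety immediately".
- **Last dose, minimum only.** Section 10.1.1: "Adverse event monitoring should be continued for at least 30 days following the last dose of study treatment". The AE and SAE rows of Table 8-1 run to a minimum of "30 days after the last dose of INC280".
- **Permanent stop.** The rule in 10.1.3 for enrolled or treated participants collects SAEs "until 30 days after the participant has permanently stopped study treatment".
- **EOT visit.** Section 8.6.1: "All subjects will be followed for AEs and SAEs for at least 30 days following the EOT visit".

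After the 30-day period, 10.1.3 asks for an SAE only where the investigator suspects the study drug.

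Four other provisions matter here. Surgery is planned up to 2 weeks after the last neoadjuvant dose (section 3). Table 8-1 adds: "Delay to the surgical procedure beyond 2 weeks is acceptable, but should be avoided". Restart is allowed up to 10 weeks after surgery (6.5.1), or 26 weeks with adjuvant chemotherapy (6.2.1.1), and treatment is permanently discontinued if that window is missed. Section 6.5.1 also states: "Participants who discontinue the study due to a surgery related AE must complete the EOT visit and safety follow-up visit". Appendix 2 (16.2.4.2) places the EOT visit no more than 7 days after the last study treatment.

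**The concern.** The design has a planned drug-free interval around surgery. Section 6.5.1 excludes it from the rule that stops treatment after 21 days without drug, so a participant in the interval has not discontinued. If restart is later ruled out, the preoperative dose becomes the last dose in retrospect, and the clock that starts from it may already have closed. The EOT visit, and on one reading the date of permanent stopping, come later.

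The same postoperative SAE can then be reportable under 8.6.1 and not under the first paragraph of 10.1.3. Table 8-1 schedules the 30-day safety visit from the last dose, so that visit can fall before the EOT visit it is meant to follow. Section 9.2 defines study completion by the 30-day safety follow-up.

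Safety and tolerability is a secondary objective, and section 1.2 states an expectation about how the drug's adverse event profile bears on surgery. An SAE that was never collected cannot be recovered by any choice of analysis period.

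**Working it through.** The documents give no derived figure on this point to reproduce, so the check is date arithmetic.

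**Inputs**
- Length of the window: 30 days (6.5.2, 8.6.1, 10.1.1, 10.1.3, Table 8-1).
- *s*, days from last neoadjuvant dose to surgery: planned at up to 14 (section 3), with no outer limit on delay (Table 8-1).
- *e*, days from surgery to the EOT visit. The documents do not fix this for non-restarters, so it is an assumption. The restart limits are 10 × 7 = 70 days and 26 × 7 = 182 days.

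**Formulas**
- The last-dose clock closes on postoperative day 30 − *s*.
- The EOT clock (8.6.1) closes on postoperative day *e* + 30.
- The difference is (*e* + 30) − (30 − *s*) = *e* + *s*.

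**Last-dose clock for a participant who never restarts**

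| *s* | Closes on postoperative day |
|---|---|
| 1 | 30 − 1 = 29 |
| 7 | 30 − 7 = 23 |
| 14 | 30 − 14 = 16 |
| 21 (delayed) | 30 − 21 = 9 |
| 28 (delayed) | 30 − 28 = 2 |

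**EOT clock, with *s* = 14**

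| Assumed EOT visit | *e* | Closes on postoperative day | Later than last-dose clock by |
|---|---|---|---|
| 7 days after last dose (Appendix 2) | 7 − 14 = −7 | 23 | 7 days |
| 2-week post-surgery visit | 14 | 44 | 28 days |
| 10-week restart limit | 70 | 100 | 84 days |
| 26-week restart limit | 182 | 212 | 196 days |

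The 26-week row is the least firm. Sections 8.6.1 and 10.1.3 narrow collection to drug-related SAEs once a new antineoplastic therapy starts, and the text does not say whether the permitted adjuvant chemotherapy counts as one.

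The Appendix 2 row shows why the rules agree for participants who restart: an EOT visit within 7 days of the last dose keeps the clocks within 7 days of each other. For a non-restarter with surgery on day 14, that row puts the EOT visit 7 days before the operation. It cannot be met when the decision not to restart is made after surgery.

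**Permanent-stop rule.** If the date of stopping is read as the date restart is ruled out, this rule follows the EOT clock. If it is read as the date of the last dose, it follows the other. The text does not settle which is meant, so the two rules in 10.1.3 can disagree.

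**Worked case.** With surgery on day 14 and the EOT visit at the 2-week post-surgery visit, a new SAE on postoperative days 17 to 44 that is judged unrelated falls inside 8.6.1 and outside the first paragraph of 10.1.3.

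**The case against.** The case on the other side is substantial, and much of it stands.

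- **Minimum versus end.** A reader might infer that most sections close collection 30 days after the last dose. They do not. Table 8-1 and 10.1.1 set minimums, and collecting to 30 days after EOT satisfies both. Only 6.5.2 and the first paragraph of 10.1.3 set an end. Equally, a minimum does not choose an anchor.
- **Nobody knows the clock is running.** While restart is still planned, a site has no ground for treating the preoperative dose as the last one, so SAEs in that period should be reported. The 84 and 196 days are therefore differences between stated end dates, not periods shown to be without reporting. The conflict applies once restart has been ruled out.
- **Known events are covered.** AEs that lead to discontinuation are followed until they resolve or stabilise (6.5.2, 8.6.1), and complications and progression of a reported SAE must be sent within 24 hours (10.1.3). A postoperative SAE that prevents restart and later proves fatal is captured. Section 8.5.1 collects surgery-related safety information on its own form, and SAP 2.8.2 takes account of deaths whenever they occurred. None of these provisions sets the end date for new SAEs.
- **Section 8.6.1 already gives the longer rule.** That is true, but 10.1.3 carries the mandatory 24-hour duty, and its first paragraph gives the shorter one.
- **Risk among non-restarters.** It is tempting to say that these participants are the most likely to have had serious complications. The documents give no reasons or rates for failure to restart, so this is unsupported.

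**Conclusion.** The rules conflict as written. For a participant who does not restart, they give different last dates for reporting a new postoperative SAE that is not suspected to be drug-related.

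Postoperative day 16 is the shortest closing date inside the planned surgical window. It is not a typical value: the range is 16 to 29, with shorter times only if surgery is delayed, which the protocol discourages and which requires contact with the sponsor. The differences of 28 and 84 days assume surgery on day 14 and an EOT visit at 2 or 10 weeks after surgery.

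A reader might infer that SAEs or deaths have been missed. Nothing in the documents shows this. The practical reach is small: SAP section 4 reports 4 participants enrolled, recruitment stopped, and data to be listed as captured. SAP 2.8.1 still tabulates SAEs for registry posting, so completeness of collection matters for those four.

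**What to change.** Reconcile 6.5.2, Table 8-1, 8.6.1, 10.1.1, both rules in 10.1.3 and Appendix 2 (16.2.4.2) to one reporting anchor. One candidate is the later of 30 days after the last capmatinib dose and 30 days after the EOT visit, since 8.6.1 already requires the second. State how the EOT visit is dated for a participant who does not restart, and schedule the 30-day safety visit after it. State also whether the permitted adjuvant chemotherapy counts as new antineoplastic therapy for AE/SAE collection.

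For the participants already enrolled, check whether any did not restart. If so, confirm that their AEs and SAEs were recorded to the reconciled date.

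The cost is protocol wording and extra AE recording for non-restarters only: 28 / 7 = 4 weeks if EOT falls at the 2-week post-surgery visit, and up to 84 / 7 = 12 weeks at the 10-week limit. Part of that time passes while restart is still planned. No new procedure is needed.
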